5.5.1 Racial/Ethnic Subgroup Analysis

The racial/ethnic composition of patients of women recruited into the MFMU Network trials varies. Assuming for this trial that the composition is 25% African-American and 30% Hispanic, similar to the ongoing STAN trial, there is limited power (40-50%) to detect a 50% reduction in the primary outcome or cesarean in the separate subgroups.

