5.5.1 Racial/Ethnic Subgroup Analysis

The racial/ethnic composition of patients of women recruited into the MFMU Network trials varies. Assuming for this trial that the composition is 25% African-American and 30% Hispanic, similar to the ongoing STAN trial, there is limited power (40-50%) to detect a 50% reduction in the primary outcome in the separate subgroups.

6 Data Collection

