2.2 Complications of Term Pregnancies beyond 39 Weeks of Gestation

2.2.1 Maternal Complications

Several studies have demonstrated that certain maternal complications increase in a continuous fashion after 37-38 completed weeks.³⁻⁸ Investigators have reported that pregnancies that continue beyond 39 weeks are associated with increased risks of cesarean section, operative vaginal delivery, 3rd and 4th degree lacerations, and chorioamnionitis.^{3-7,9}

Table 1 summarizes the maternal data from the largest and most recent cohort studies that have examined adverse outcomes in term pregnancies. Most of these studies examined maternal complications in multivariable models and found that gestational age beyond 39 weeks was predictive of increased risk even when controlling for known confounders such as maternal age, ethnicity, education, parity, length of labor, induction, and birth weight.

Table 1. Maternal Complications in Singleton Gestation by Gestational Week

Population and Reference	39 weeks	40 weeks	41 weeks	Adjusted OR (95% CI) 41 wks vs 39 wks in a Multivariable Model
Primary cesarean delivery (multiparas and nulliparas)				
N=45,673; 1992-2002 ⁴	14.0%	15.9%**	21.2%**	1.32 (1.17, 1.53)
N=32,828; low risk; 1976-2001 ³	9.2%	10.4%**	14.1%**	1.44 (1.28, 1.62)
N=119,254; low risk; 1995-99 ⁵	8.8%	9.0%	14.0%**	1.28 (1.20, 1.36)
N=2,928,722; low risk; from US natality data 2003 ⁷	12.8%	14.1%**	19.8%**	1.46 (1.44, 1.48)
Primary cesarean delivery rates by weeks' gestation in nulliparas only				
N=32,828; low risk; 1976-2001 ³	11.4%	14.2%*	18.9%**	Not available
N=119,254; low risk; 1995-99 ⁵	14.4%	14.9%	21.9%**	Not available
N=2,928,722; low risk; from US natality data 2003 ⁷	21.5%	23.3%**	30.1%**	Not available
Operative vaginal delivery				
N=45,673; 1992-2002 ⁴	15.5%	17.9%**	18.5%	1.14 (1.05, 1.23)
N=32,828; low risk; 1976-2001 ³	14.8%	16.4%**	17.4%**	1.22 (1.10, 1.44)
N=119,254; low risk; 1995-99 ⁵	9.4%	10.9%**	13.3%**	1.29 (1.20, 1.36)
N=2,928,722; low risk; from US natality data 2003 ⁷	7.6%	8.1%**	9.6%**	1.14 (1.11, 1.16)
3rd and 4th degree lacerations				
N=32,828; low risk; 1976-2001 ³	9.4%	10.8%**	12.0%**	1.26 (1.10, 1.44)
N=119,254; low risk; 1995-99 ⁵	4.0%	4.6%*	6.7%**	1.58 (1.44, 1.73)
Postpartum hemorrhage				
N=32,828; low risk; 1976-2001 ³	13.4%	12.8%	16.0%**	1.18 (1.06, 2.31)
N=119,254; low risk; 1995-99 ⁵	2.5%	3.1%**	4.1%**	1.21 (1.10, 1.32)
Febrile morbidity				
N=45,673; 1992-2002 ⁴	1.7%	2.3%	2.7%**	1.46 (1.14, 1.87)

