outcomes. Moreover, these studies have typically evaluated women undergoing induction versus those undergoing spontaneous labor; this comparison is inappropriate and not clinically relevant,³⁶ as spontaneous labor is not a choice but an event. Indeed, many women who are not “induced” at a given gestational age will ultimately require induction or oxytocin augmentation at a later gestational age, or experience an obstetric complication which itself may be associated with a risk of adverse neurodevelopmental outcome, a risk that may have been prevented had the women been induced earlier. Thus, the clinically meaningful comparison is labor induction versus expectant management. Yet, there are no data that suggest that elective induction compared with expectant management increases the risk of neurodevelopmental disorders or other adverse long-term outcomes.

Table 3. Randomized Controlled Trials of Elective Induction of Labor (EIOL) at 39-40 Weeks vs Expectant Management (EM)

Year and Reference	N	Patient Population (% nullips)	Gestational Age at EIOL	Gestational Age for EM	Outcome: EIOL vs. EM (p>0.05 unless noted)
1975 ³⁷	228	• Multiparous or nulliparous (46%)	39-40 weeks	41 weeks	Cesarean: 4.5% vs 7.7%
1978 ³⁸	230	• Multiparous or nulliparous*	39 weeks	42 weeks	Cesarean: 4.3% vs 1% Operative vaginal delivery: 18.5% vs 20.7%
1979 ³⁹	112	• Multiparous or nulliparous (45%)** • Favorable cervix	40 weeks	42 weeks	Operative vaginal delivery: 2.3% vs 4.8%
1989 ⁴⁰	345	• Multiparous or nulliparous (54%) • Favorable cervix	40 weeks	42 weeks	Nulliparas: Cesarean: 1.0% vs 3.4% Operative vaginal delivery: 3.0% vs 3.4% Multiparas: Cesarean: 1.2% vs 0% Operative vaginal delivery: 1.2% vs 0%
1999 ⁴⁰	194	• Nulliparous [†]	39 weeks	42 weeks	Cesarean: 6.4% vs 5.6% Operative vaginal delivery: 53.4% vs 33.3% (p=.03)
2005 ⁴¹	226	• Multiparous or nulliparous (45%) • Favorable cervix	39-40 weeks	42 weeks	Nulliparas: Cesarean: 13.3% vs 10.3% Multiparas: Cesarean: 2.8% vs 3.8%

* Excluded women in EIOL group who had spontaneous labor before 39 weeks and women in EM group if failed to go into spontaneous labor by 42 weeks

** Excluded women in either group with spontaneous labor before 40 weeks or who required a cesarean

† Excluded women in EIOL group who had spontaneous labor before 39 weeks and women in EM group if induced before 42 weeks or failed to go into spontaneous labor by 42 weeks

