5.2.2 Cesarean Delivery

Assuming that the rate of cesarean delivery is 30% in the expectant management group, a sample size of 6000 women also yields more than 90% power to detect a nominal 15% increase or decrease even after adjusting for 7.5% crossovers.

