5.5 Analysis Plan

All statistical analyses will be based upon the total cohort of patients randomized into the trial. Although data on some patients may be missing, all relevant data available from each patient will be employed in the analyses. Patients will be included in the treatment group to which they were randomly assigned regardless of compliance.

The primary analysis will consist of a simple comparison of binomial proportions. The relative risk and confidence interval will be reported. The individual components of the composite outcome will also be examined. If the treatment groups are found to differ on a pre-treatment factor known to be a risk factor for the outcome, the statistical analysis will adjust for these differences. An evaluation of treatment by center interaction will be included. An analysis adjusting by center also will be performed to ensure that center differences do not change the conclusion.

If the two groups show a difference in the incidence of the primary outcome or cesarean, interactions will be evaluated and subgroup analyses conducted to determine whether the effect prevails throughout

particular subgroups of patients. Indeed, NIH guidelines require investigators to evaluate consistency between the genders and across racial subgroups (see Section 5.5.1). It should be noted, however, that subgroup analyses have been greatly abused, particularly when there is no overall treatment difference.⁵² There is a strong temptation to search for a specific subpopulation in which the therapy is nevertheless effective. Yusuf et al. concluded “*the overall ‘average’ result of a randomized clinical trial is usually a more reliable estimate of the treatment effect in the various subgroups examined than are the observed effects in individual subgroups.*”⁵³ Thus subgroup analyses will be interpreted with care.

It is generally acknowledged that subgroup analysis that is pre-specified in the protocol has more validity than ad-hoc comparisons. The following factors will be considered for subgroup analysis, if there is a significant interaction between the factor of interest and the treatment effect.

- Race/ethnicity (see below)
- Modified Bishop score (< 5 and ≥ 5)
- Body mass index (obese and non-obese)
- Maternal age (< 35 and ≥ 35 years)
- Admitting provider specialty (see below)

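### Section 5.5.1 gives 40-50% subgroup power for halving cesarean delivery; at the plan's own 30% rate that power is above 99.9%

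*Combined protocol and SAP*

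**What the plan says.** Section 5.5.1 of the current protocol assumes that 25% of participants are African-American and 30% Hispanic, and concludes that "there is limited power (40-50%) to detect a 50% reduction in the primary outcome or cesarean in the separate subgroups". The initial protocol gives the same range under the same heading for the primary outcome alone: "there is limited power (40-50%) to detect a 50% reduction in the primary outcome in the separate subgroups". The list of protocol changes dates the addition of cesarean to April 2017. The power range was not altered.

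Section 5.2.2 sets the planning value for cesarean: "Assuming that the rate of cesarean delivery is 30% in the expectant management group". It states that the full sample of 6000 "yields more than 90% power to detect a nominal 15% increase or decrease even after adjusting for 7.5% crossovers". The primary outcome is planned at 3.5% under expectant management (Appendix A).

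In section 5.5 of the current protocol, cesarean is one of two outcomes that lead to subgroup work: "If the two groups show a difference in the incidence of the primary outcome or cesarean, interactions will be evaluated and subgroup analyses conducted". Each listed factor is then taken up only "if there is a significant interaction between the factor of interest and the treatment effect".

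**The concern.** For a fixed sample size and a fixed relative reduction, power rises steeply with the control rate. An outcome planned at 30% and one planned at 3.5% cannot share a 40-50% range for a halving. Section 5.2.2 points the same way: it claims more than 90% power for a 15% change with 3000 per arm. A subgroup has a quarter or more of that number, and the effect in question is more than three times as large.

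What is at stake is interpretation. A reader who relied on section 5.5.1 could dismiss a null cesarean result in a racial or ethnic subgroup as underpowered even for a halving. On the plan's own inputs, the trial would almost certainly detect one.

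**Working it through.** **Inputs.**
- N = 6000, allocated 1:1, so 3000 per arm (sections 3.6 and 5.2.1).
- Subgroup shares of 25% and 30% (section 5.5.1): 0.25 × 3000 = 750 and 0.30 × 3000 = 900 per arm.
- Two-sided 5% test; crossover x of 7.5%, range 5-10%, with crossovers taking the induction-arm rate (section 5.2.1). I also ran x = 0.
- Cesarean 30% (section 5.2.2); primary outcome 3.5% (Appendix A).
- Assumption: the 30% rate applies within each subgroup.

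**Formulas.** With nominal control rate p and induction rate p2, the control rate after crossover is p1 = p(1 − x) + p2·x. The pooled two-proportion power is Φ[(|p1 − p2| − 1.96·s0)/s1], where s0 = √(2p̄(1 − p̄)/n), p̄ = (p1 + p2)/2 and s1 = √((p1(1 − p1) + p2(1 − p2))/n). I also used the unpooled test, the pooled test with continuity correction, the log relative risk, and a formula with variance (p1 + p2)/n. The last reproduces all 96 cells of Table 6.

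**Reproducing the plan's own figures.**
- *Section 5.2.2* (n = 3000, 15% change, x = 7.5%). The decrease is 0.2966 vs 0.255 and the pooled test gives 95.0%. The increase is 0.3034 vs 0.345 and gives 93.1%. Both agree with the plan. The (p1 + p2)/n formula gives 86.6% and 80.8%, which do not, so the pooled test is the suitable one for cesarean.
- *Section 5.5.1, primary outcome* (3.5% halved, x = 0-10%, all formulas): 43-56% with 750 per arm and 51-64% with 900. With continuity correction and x = 10% the values are 42.7% and 50.6%. The stated range is roughly right for this outcome, and I do not challenge it.

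**Cesarean, 50% reduction** (p2 = 0.15).
- x = 7.5%, pooled, n = 750: p1 = 0.30 × 0.925 + 0.15 × 0.075 = 0.28875; s0 = 0.02137, s1 = 0.02107; (0.13875 − 1.96 × 0.02137)/0.02107 = 4.60, so power is 99.9998%.
- Least favourable case, x = 10% with variance (p1 + p2)/n, n = 750: p1 = 0.285; 0.135/√(0.435/750) − 1.96 = 3.65, so power is 99.987%. With n = 900 the value is 4.18, so power is 99.998%.

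**Sensitivity to the control rate** (halving, range over formulas and x = 0-10%):

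| Control rate | Source | 750 per arm | 900 per arm |
|---|---|---|---|
| 30% | Section 5.2.2 | ≥ 99.98% | ≥ 99.99% |
| 11.4% | Table 1, lowest nulliparous rate | ≥ 93% | ≥ 96% |
| 10.3% | Table 3, nulliparas, 2005 trial | 91-96% | 95-98% |
| 5.6% | Table 3, nulliparas, 1999 trial | 65-77% | 74-84% |
| 3.4% | Table 3, nulliparas, 1989 trial | 41-55% | 49-63% |

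**What 40-50% would correspond to.**
- For a halving, a control rate of about 1.9-4.1%, which is the range of the rare primary outcome.
- At a 30% rate, a reduction of about 12-19% over all five formulas.
- At 30% vs 15% without crossover, only about 46-60 women per arm (pooled test).

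**Cesarean, 15% reduction, x = 7.5%** (0.2966 vs 0.255). The pooled test gives 43.8% (750 per arm) and 50.6% (900 per arm). Over all five formulas the ranges are 34-44% and 39-51%; the low ends come from the formula that does not fit section 5.2.2.

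**The case against.** The strongest reply is that nothing depends on the sentence. It is descriptive, it errs on the cautious side, and subgroup results are reported only after a significant interaction, so within-subgroup power opens or closes no analysis. Its practical message is also right at the only cesarean effect the plan names: for a 15% reduction, pooled power is 43.8% and 50.6%, almost the stated range. All of this stands and keeps the point minor. It does not make the sentence correct, because the effect stated is 50%.

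Subgroup cesarean rates are not given and could differ from 30%. That is true, but a halving has 40-50% power only at control rates of about 1.9-4.1%. In Table 3, only the 3.4% in the 1989 trial's nulliparas falls that low among the nulliparous expectant-management rates. That was a small trial restricted to women with a favorable cervix, and this protocol plans on 30%.

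The figure might be meant as the power of the interaction test. The sentence speaks of detecting a reduction in the separate subgroups, which is a two-arm comparison within each. Interaction power is a separate matter: a halving that was uniform across groups need not give a significant interaction at all. If the halving were confined to one subgroup, with a 15% reduction elsewhere, interaction power would be about 99.6% and 99.9%, so that reading does not yield 40-50% either.

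**Conclusion.** The concern holds. On the plan's own rate, sample size and crossover, power to detect a halving of cesarean within either subgroup exceeds 99.9%, so the stated range is too low by about 50 percentage points. No formula or crossover value tried gives 40-50%. The result assumes a 30% cesarean rate within subgroups and survives a fall to 11.4%. It concerns the within-subgroup comparison only, and the primary-outcome half of the sentence is not in dispute. The likely cause is that cesarean was added to an existing sentence without recalculating its power. Severity is minor.

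**What to change.** The better remedy is to keep the existing range for the primary outcome and add a separate cesarean sentence that names its assumptions. For example: *For cesarean (30% rate, 7.5% crossover, pooled two-proportion test without continuity correction, two-sided 5%), power within a subgroup exceeds 99% for a 50% reduction and is about 44% (25% subgroup) to 51% (30% subgroup) for a 15% reduction.* The pooled test is suggested because it agrees with section 5.2.2.

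The shorter remedy is to remove cesarean from the sentence. That corrects the error but leaves no subgroup power statement for an outcome that opens subgroup analysis.

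Either change costs a few words. No operational procedure, sample size or analysis changes.

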5.5.2 Admitting Provider Specialty Subgroup Analysis

Although admitting provider specialty is not a baseline variable, this variable will be evaluated for subgroup analysis if the two groups show a difference in the incidence of the primary outcome or cesarean, and if the test for interaction is significant. Elective induction of labor may be perceived as an intervention more likely utilized by obstetricians than by midwives, therefore it is important to demonstrate whether a treatment effect is present among patients treated by obstetricians and among patients treated by midwives.

6 Data Collection

6.1 Data Collection Forms

Data will be collected on standardized forms on which nearly all responses have been pre-coded. Each form is briefly described below:

- AR01 Screening Log.
- AR02 Eligibility and Randomization Form is completed for all patients eligible and consenting for the study, and documents the project gestational age and randomization digital cervical exam.
- AR04 Baseline Form is completed for all randomized patients. This form includes detailed demographic and social data, and medical and obstetrical history.
- AR05 Clinic and Hospital Visit Log documents scheduled and unscheduled clinic, urgent care and hospital visits, procedures and diagnostic tests, including the antepartum portion of the delivery admission.
- AR08 Labor and Delivery Summary Form documents specific pregnancy complications since randomization, in addition to labor, delivery and postpartum information.
- AR08A Labour Agency Questionnaire
- AR09 Neonatal Baseline Form records date and time of birth, delivery data and status at delivery, for each fetus/infant.
- AR10 Neonatal Outcome Form records outcome data for all infants admitted to the NICU or special care nursery.
- AR11 Patient Status Form documents loss to follow up/withdrawal status, last date of contact for lost to follow-up patients.
- AR12 Adverse Event Form records serious and non-serious adverse events.
- AR13 Postpartum Follow-up Form
- AR13A Maternal Follow-up Log documents the reasons and diagnoses associated with maternal clinic, urgent care and hospital visits
- AR13B Infant Follow-up Log documents the reasons and diagnoses associated with infant clinic, urgent care and hospital visits

6.2 Web Data Entry System

For this protocol, web data entry screens corresponding to the study forms listed above will be developed and maintained by the staff of the BCC. Clinical center staff will enter data into the MySQL database located at the BCC through a web data management system (MIDAS). The data are edited on-line for missing, out of range and inconsistent values. A Users' Manual documenting this system is provided to the centers by the BCC.

6.3 Centralized Data Management System

Daily data conversions from the MySQL database create up-to-date SAS datasets. Data are reviewed weekly using edit routines similar to those implemented on-line during data entry, as well as additional checks for data consistency within or across forms. A database of resulting potential data problems is

generated in MIDAS for initial review by BCC staff, who then evaluate the comments keyed in association with edits on missing or unusual values. Valid edits will be flagged in MIDAS for resolution at the clinical centers.

At regular intervals, specialized data reviews comparing data availability and consistency across forms are run by the BCC staff on the entire database or on a specific subset of data. These reports are also submitted to the centers for correction or clarification.

An audit trail, consisting of all prior versions of each data form as entered in the computer for each patient, is maintained so that the succession of corrections can be monitored.

6.4 Performance Monitoring

The BCC will present regular reports to the ARRIVE Subcommittee, the Steering Committee, and the Data and Safety Monitoring Committee. These include:

- Monthly Recruitment Reports - reports of the number of women screened and enrolled by month and by clinical center are provided monthly to the ARRIVE Subcommittee and all other members of the Steering Committee. Weekly or bi-weekly reports are provided electronically if needed.
- Quarterly Steering Committee Reports - reports detailing recruitment, baseline patient characteristics, data quality, incidence of missing data and adherence to study protocol by clinical center, are provided quarterly to the ARRIVE Subcommittee and all other members of the Steering Committee.
- Data and Safety Monitoring Committee Reports - for every meeting of the DSMC, a report is prepared which includes patient recruitment, baseline patient characteristics, center performance information with respect to data quality, timeliness of data submission and protocol adherence (in addition to safety and efficacy data). The reports also include adverse events, loss to follow-up and all outcome variables as described previously in this protocol.

7 Study Administration

7.1 Organization and Funding

The study is funded by the *Eunice Kennedy Shriver* National Institute of Child Health and Human Development (NICHD). The study is conducted by the NICHD Maternal-Fetal Medicine Units (MFMU) Network, consisting of fourteen clinical centers, the Biostatistical Coordinating Center (BCC) and the NICHD, and is administered under cooperative agreements between each of the centers and the NICHD. Each of the funded institutions is represented by a Principal Investigator. A complete description of the organization of the MFMU Network is provided in the MFMU Network Policy Manual.

7.1.1 Participating Clinical Centers

The participating Principal Investigators of the clinical centers have agreed to abide by the study protocol, to have comparable staff, facilities and equipment and to ensure the proper conduct of the study at each of their centers including: recruitment and treatment of patients as specified in the protocol, accurate data collection and the transmission of information to the Steering Committee.

7.1.2 Biostatistical Coordinating Center

The BCC is responsible for all aspects of biostatistical design, data management, interim and final statistical analyses, and preparation of publications based on the study results. The Principal Investigator of the BCC reports to the Steering Committee and the Data and Safety Monitoring Committee.

7.1.3 NICHD

In addition to its role as funding agency, the NICHD participates in the activities of the Network, including the development of protocols, administration and conduct of the studies and preparation of publications.

7.1.4 Network Advisory Board

Appointed by the NICHD, the members of the Network Advisory Board consist of a group of experts who are not affiliated with research being conducted by the Network and represent the disciplines of maternal-fetal medicine, neonatology and biostatistics/epidemiology. The role of the board includes the review and prioritization of proposed studies, in addition to the identification of scientifically and clinically important questions and ideas that might be conducted by the Network. The NICHD Project Scientist convenes and attends the meetings.

7.2 Committees

7.2.1 Steering Committee

This committee consists of seventeen members. The Principal Investigator from each of the fourteen clinical centers, the BCC, and the NICHD MFMU Network Project Scientist are all voting members. The Chair of the Steering Committee may vote to break a tie. The Chair, a person independent of the participating institutions, is appointed by NICHD. The Steering Committee has the responsibility for identifying topics for Network studies, designing and conducting study protocols and monitoring study implementation, recruitment and protocol adherence. The committee receives recommendations from the Data and Safety Monitoring Committee and the Network Advisory Board.

